1. PROTOCOL SUMMARY

Protocol Title: A Randomized Open-Label Phase 1/2 Study of INCB001158 Combined With Subcutaneous (SC) Daratumumab, Compared to Daratumumab SC, in Participants With Relapsed or Refractory Multiple Myeloma

Protocol Number: INCB 001158-206

Objectives and Endpoints:

[Table 1](#) presents the primary objectives and endpoints.

Table 1: Primary Objectives and Endpoints

Objectives	Endpoints
Primary	
Phase 1: To determine the safety, tolerability, and RP2D of INCB001158 in combination with daratumumab SC.	Safety and tolerability determined by monitoring the frequency, duration, and severity of AEs.
Phase 2: To compare the ORR of the RP2D of INCB001158 in combination with daratumumab SC to daratumumab SC monotherapy.	ORR, defined as the proportion of participants with a documented response PR or better, as per IMWG criteria.

Overall Design:

[figure not shown]
This study will evaluate the safety and efficacy of INCB001158 in combination with daratumumab SC in participants with relapsed or refractory MM, based on the hypothesis that INCB001158 in combination with daratumumab SC will improve response rates compared with daratumumab SC alone.

[Table 2](#) presents the key study design elements. Further details are presented after the table in the study design schema (see [Figure 1](#)).

Table 2: Key Study Design Elements

Study Phase	Phase 1/2
Clinical Indication	Multiple myeloma
Population	Male and female participants \geq 18 years of age who have relapsed or refractory MM.
Number of Participants	Phase 1: Approximately up to 18 evaluable participants will be enrolled. Phase 2: Approximately up to 80 evaluable participants will be enrolled.
Study Design	Open-label, dose-escalation Phase 1 and randomized Phase 2 study.
Estimated Duration of Study Participation	Up to 28 days for screening, continuous treatment in consecutive 28-day cycles as long as participants are receiving benefit and have not met any criteria for study withdrawal, and every 8 to 12 weeks for follow-up. NOTE: As of Protocol Amendment 3, no further disease status and survival follow-up assessments will be required beyond the last safety follow-up visit.
Coordinating Principal Investigator	[REDACTED], MD

Figure 1: Study Design Schema

Treatment Groups and Duration:

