4.1.1. Phase 1: Dose Escalation of INCB001158 + Daratumumab SC

In Phase 1, INCB001158 in combination with daratumumab SC will be administrated in 28-day treatment cycles, and study treatment is summarized in [Table 9](#).

Table 9: Study Treatment for Participants in Phase 1 Dose Escalation

Study Treatment	INCB001158	Daratumumab SC
	50-100 mg PO BID continuous dosing until disease progression, unacceptable toxicity, or discontinuation from study treatment for any other reason.	1800 mg SC co-formulated with rHuPH20 (2000 U/mL). Administration is once weekly for Cycles 1 and 2, once every 2 weeks for Cycles 3 to 6, and then once every 4 weeks until disease progression, unacceptable toxicity, or discontinuation from study treatment for any other reason.

BID = twice daily; IV = intravenous; PO = orally; SC = subcutaneous.

Dose escalation of INCB001158 will begin at a starting dose 75 mg BID, which is 1 dose level below the RP2D for both monotherapy and combination with PD-1 inhibitor (per study INCB 01158-101) and for combination with chemotherapy (per study INCB 01158-203) in participants with advanced/metastatic solid tumors. The starting dose of 75 mg BID is also 2 dose levels below the highest dose (150 mg BID) tested in the INCB 01158-101 study, while the MTD has not been reached (see [Section 2.2.3](#)).

The doses of INCB001158 to be evaluated and scenarios for dose escalation and de-escalation are summarized in [Table 10](#).

Table 10: INCB001158 Dose Levels

INCB001158 Dose Level	INCB001158 Dose
-1	50 mg BID
1 (starting dose)	75 mg BID^a
2	100 mg BID

BID = twice daily.

^a If INCB001158 75 mg BID is not tolerated, INCB001158 50 mg BID may be evaluated.

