Dose escalation and de-escalation in Phase 1 will follow the BOPIN design algorithm (Yuan and Liu 2016). Given the target DLT rate of 33% for INCB001158 in combination with daratumumab SC, the dose escalation and de-escalation rules are shown in Table 11. The BOPIN design also includes an elimination rule. When ≥ 3 participants have been treated, if the probability that the estimated toxicity rate that is above the target DLT rate is $> 95\%$ at a certain dose level, then this dose level and higher dose levels are assumed to be too toxic and will be eliminated. If the lowest dose level is eliminated, then the whole dose escalation will be terminated. Table 11 (in the bottom row) provides the elimination rules. Based on this algorithm, a minimum of 3 evaluable participants and a maximum of 9 evaluable participants will be enrolled at each tested dose level. The dose escalation will continue, based on the rules in Table 11, until at least 1 of the following occurs:

- Enrollment of additional participants at a dose level that already has 9 evaluable participants.
- Dose escalation to a dose level that has already been eliminated.
- Dose escalation above 100 mg BID.

At that point, the dose escalation will be stopped.

Table 11: Dose Escalation, De-Escalation, and Elimination Boundaries for Target DLT Rate of 33% in Phase 1

Action	Number of Evaluable Participants Treated at the Current Dose								
	1	2	3	4	5	6	7	8	9 ^a
Escalate if # of DLTs \leq	0	0	0	1	1	1	1	2	2
De-escalate if # of DLTs \geq	1	1	2	2	2	3	3	4	4
Elimination if # of DLTs \geq	N/A	N/A	3	3	4	4	5	5	6

DLT = dose-limiting toxicity; N/A = not applicable.

^a If 9 evaluable participants are enrolled at a dose level, and 3 of those participants experience a DLT, then the medical monitor and the investigators will review the entirety of the data and decide whether to escalate the dose level, de-escalate the dose level, or stop at that dose level.

The INCB001158 dose will be escalated using an open-label BOPIN design and a PAD or the MTD will be determined, or the maximum dose of INCB001158 (100 mg BID) will be reached.

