A PAD of INCB001158 is defined as a dose that achieves a C_{min} of INCB001158 at steady state of $\geq 1 \mu\text{M}$ that is equivalent to the IC_{90} for arginase 1. The MTD is the maximum tolerated or tested dose of INCB001158, such that fewer than 33% of the participants receiving the combination experience a DLT during the first 28 days on study drug. After the dose escalation is completed, one of the INCB001158 dose levels that is pharmacologically active and tolerable in combination with daratumumab SC (ie, MTD or lower), will be selected as the RP2D.

Dose interruptions and/or modifications may be implemented based on toxicity. Dose modifications should not be made during the DLT observation period without discussion with the medical monitor. Intraparticipant dose escalation is not permitted. At the discretion of the sponsor, up to 6 additional "backfill" participants may be enrolled at any tolerable dose level to further investigate safety, efficacy [REDACTED].

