10. STATISTICS

10.1. Sample Size Determination

10.1.1. Sample Size for Phase 1

In Phase 1, the BOPIN design will be used to determine the RP2D of INCB001158 given in combination with daratumumab SC, in participants with relapsed or refractory MM. Dose escalation and de-escalation will follow the BOPIN design algorithm. Based on this algorithm, a minimum of 3 evaluable participants and a maximum of 9 evaluable participants will be enrolled at each tested dose level, so up to 18 evaluable participants will be enrolled in Phase 1. The details of the dose escalation, de-escalation, and elimination rules according to the BOPIN design are provided in Section 4.1.1.

10.1.2. Sample Size for Phase 2

In Phase 2, the sample size will be guided by the RAR design based on a Bayesian beta-binomial model, which will include within individual treatment groups early termination rules for efficacy and early stopping rules for safety. The proposed RAR design has an expected frequentist 1-sided Type I error of approximately 10% and power of 78% to detect an improvement in response from 20% to 45%. The response rates for each treatment group will be estimated with 90% Bayesian credible intervals.

The expected number of participants accrued each month is 4, and the expected number of months between treatment and assessment of response is 3. The simulation results for various Treatment Group A response rates are presented in [Table 26](#).

Table 26: Estimates of Operating Characteristics for Response Adaptive Design

True Response Rate: Treatment Group A	True Response Rate: Treatment Group B	Probability to Reject Null Hypothesis (Early Termination)	Expected Sample Size in Treatment Groups A, B, and C (Treatment Group A)	Average Study Duration in Months
20%	20%	9.8% (1.2%)	79.7 (34.7)	22.9
35%	20%	50.1% (12.1%)	76.6 (41.4)	21.8
40%	20%	65.7% (19.8%)	74.5 (41.5)	21.0
45%	20%	78.7% (30.0%)	71.7 (40.6)	20.0

Note: For each simulated study replication, the first 30 participants were equally randomized among Treatment Groups A, B, and C, and the next 50 participants were randomized among Treatment Groups A and B using RAR. Sample size and study duration estimates were based on projected enrollment of 4 participants per month and the time to response of 3 months. Estimates were based on simulation of 300,000 study replications.

Descriptive statistics for the ORR, DOR, and other efficacy parameters for Treatment Group C will be provided.

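### The stated Phase 1 maximum of 18 evaluable participants assumes two dose levels, but the protocol allows three, which puts the ceiling at 27

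*Protocol*

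**What the plan says.** Protocol Section 10.1.1 states that, under the Bayesian optimal interval (BOIN) algorithm, "a minimum of 3 evaluable participants and a maximum of 9 evaluable participants will be enrolled at each tested dose level", and draws from this, "so up to 18 evaluable participants will be enrolled in Phase 1". Table 2 in the Protocol Summary repeats the number with a qualifier: "Phase 1: Approximately up to 18 evaluable participants will be enrolled".

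Section 4.1.1 describes the dose ladder:

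- The start is the middle level: "Dose escalation of INCB001158 will begin at a starting dose 75 mg BID".
- Table 10 has a level above it (100 mg BID) and a level -1 below it. The footnote on level -1 reads "If INCB001158 75 mg BID is not tolerated, INCB001158 50 mg BID may be evaluated".
- Table 9 gives the Phase 1 range accordingly: "50-100 mg PO BID continuous dosing until disease progression".
- Escalation ends when any one of three conditions is met: the next participants would go to a level that already has 9 evaluable participants; the rules call for escalation to an eliminated level; or they call for "Dose escalation above 100 mg BID".
- Separately, at the sponsor's discretion, "up to 6 additional 'backfill' participants may be enrolled at any tolerable dose level".

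SAP Section 3.3 gives no Phase 1 number of its own and refers back to the protocol.

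**The concern.** Section 10.1.1 presents 18 as a consequence of the limit of 9 per level. A limit per level gives a total only once the number of levels is fixed, and 18 corresponds to two. The ladder in Section 4.1.1 has three. Level -1 is a contingency, but a stated maximum has to cover the contingencies that the rules permit.

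What is at stake is the accuracy of a stated upper limit on exposure to a new combination. Ethics committees and sites read such a figure as a bound. As written, a site network could follow every rule in Section 4.1.1 and still enrol more evaluable participants than Section 10.1.1 says is possible. The validity of dose finding is not at stake.

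**Working it through.** **Inputs.** Maximum per tested level: 9 evaluable (Sections 4.1.1 and 10.1.1). Levels: 50, 75 and 100 mg BID, starting at 75 (Table 10). Boundaries for escalation, de-escalation and elimination: Table 11. Stopping conditions: Section 4.1.1. Cohort size is not stated in the documents; cohorts of 3 are assumed below.

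**Step 1: the plan's own figure.** Maximum = 9 x number of levels tested.

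- Two levels (75 and 100, or 75 and 50): 9 x 2 = 18, which reproduces the stated figure.
- Three levels: 9 x 3 = 27, which does not.

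**Step 2: are the Table 11 boundaries as intended?** With target rate 0.33 and the Section 10.5.1 parameters 0.6 x 0.33 and 1.4 x 0.33, the BOIN cut-offs are 0.260 (escalate) and 0.395 (de-escalate). Applied to n = 1 to 9, they give escalation limits 0, 0, 0, 1, 1, 1, 1, 2, 2 and de-escalation limits 1, 1, 2, 2, 2, 3, 3, 4, 4. Both rows match Table 11.

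**Step 3: can 27 actually be reached?** Yes. One permitted path, with cumulative DLTs / evaluable participants at each level:

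| Level | Cumulative counts | Table 11 action |
|---|---|---|
| 75 mg | 0/3 | escalate |
| 100 mg | 1/3, 2/6, 4/9 | stay, stay, de-escalate |
| 75 mg | 2/6, 4/9 | stay, de-escalate |
| 50 mg | 1/3, 2/6, 2/9 | stay, stay, escalate; 75 mg already has 9, so stop |

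Total: 9 + 9 + 9 = 27. No elimination boundary is crossed (that would need 3 of 3, 4 of 6 or 6 of 9), and no stopping condition applies before the last step.

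**Step 4: how likely is a total above 18?** Every path through Table 11 was enumerated exactly, starting at 75 mg with cohorts of 3. The DLT rates are assumptions, because the documents give none for this combination.

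| Assumed DLT rates at 50 / 75 / 100 mg | P(total > 18) | P(all three levels tested) | Expected total |
|---|---|---|---|
| 2% / 5% / 10% | 0.04% | 0.5% | 7.7 |
| 5% / 10% / 15% | 0.2% | 1.4% | 9.0 |
| 10% / 20% / 30% | 0.8% | 2.8% | 11.9 |
| 20% / 33% / 45% | 1.6% | 4.0% | 13.4 |
| 25% / 40% / 50% | 2.0% | 4.4% | 13.4 |
| 33% / 45% / 55% | 2.3% | 4.5% | 13.3 |

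A total of exactly 27 has probability of about 0.2% or less in each scenario. The ceiling of 27 itself does not depend on the assumed rates.

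**The case against.** The best defence is that 18 is right for the trial the sponsor expected to run. Level -1 opens only if 75 mg BID is not tolerated, two levels is the usual outcome, and Table 2 says approximately. No boundary, error rate or analysis is calculated from 18, because the BOIN rules work on counts per level. Enrolment had also ended by Amendment 3, and the SAP plans safety summaries and efficacy listings that do not use the Phase 1 ceiling. All of this stands, and it keeps the point small. It does not rescue the sentence in Section 10.1.1, which carries no qualifier and presents 18 as following from the limit per level.

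A reader might infer something stronger from the backfill provision: that 18 is wrong for that reason too, that the true maximum is 33 (27 + 6), or that exceeding 18 would be common. The documents do not support this.

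- Backfill participants are described as additional and discretionary, while 18 is derived from the escalation algorithm. Leaving them out of that count is not an error in it; a cross-reference is all that is missing.
- A high chance of exceeding 18 appears only if all 6 discretionary places are assumed filled and then counted against a figure they are declared to be outside. Even on that premise the answer depends on the assumed DLT rates and falls to 13.1% at 5/10/15% and 5.1% at 2/5/10%.
- A single total of 33 would add evaluable participants to backfill participants whose evaluability is not stated. It would not be an enrolment maximum either, because Section 5.5 allows non-evaluable Phase 1 participants to be replaced.

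**Conclusion.** The point holds as a minor inconsistency. Section 10.1.1 states a maximum of 18 evaluable participants that is correct for two dose levels only. With the three levels in Table 10 and no overall cap in Section 4.1.1, the ceiling is 27, which is 9 participants or 50% above the stated figure. This rests on the protocol's text and simple multiplication, and a permitted path through Table 11 reaches it.

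Exceeding 18 in escalation is unlikely: about 0.04% to 2.3%, conditional on cohorts of 3 and the DLT rates assumed above. A reader should not conclude that the dose-finding design is unsound or that the planned analysis is affected.

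**What to change.** In Section 10.1.1 and Table 2, state that Phase 1 will include up to 18 evaluable participants if two dose levels are tested and up to 27 if all three are tested, not counting up to 6 additional backfill participants. If the sponsor intended 18 as a firm limit, state it as an explicit overall cap and reconcile Sections 4.1.1 and 10.1.1 and Table 2 with it, including what happens when the cap is reached. SAP Section 3.3 needs no change, since it refers to the protocol.

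The cost is a wording change. The downside of the first option is that the stated maximum becomes larger. With enrolment closed, the benefit is an accurate record of the planned size in the protocol and the study report.

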10.2. Populations for Analysis

[Table 27](#) presents the populations for analysis.

Table 27: Populations for Analysis

Population	Description
Enrolled	All participants who sign the ICF.
FAS	All participants enrolled in the study who received at least 1 dose of study treatment (INCB001158 or daratumumab SC). Participants will be analyzed according to the treatment that they were assigned to. The FAS will be used for the summary of demographics, baseline characteristics, and disposition.
IMWG response evaluable	All participants enrolled in the study who have received at least 1 dose of study treatment (INCB001158 or daratumumab SC), completed a baseline disease assessment, and meet at least 1 of the following criteria: 
 • ≥ 1 postbaseline disease assessment • Been on the study for a minimum of 35 days of follow-up • Discontinued from treatment
DLT evaluable	All participants who receive at least 42 of 56 doses for the 28-day cycle regimen (representing $\geq 75\%$ of the dose planned) of INCB001158 at the level assigned or who have a DLT.

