8.2.1. Evaluations

8.2.1.1. Responses Categories

Assessment of tumor response and disease progression will be conducted in accordance with the IMWG response criteria. Disease evaluations will include measurements of myeloma proteins, bone marrow examinations, skeletal surveys, assessment of extramedullary plasmacytomas, and measurements of serum calcium corrected for albumin.

Efficacy/disease evaluations must be performed at each treatment cycle as specified in the SoA (see [Table 3](#) and [Table 4](#); as of Protocol Amendment 3, see [Table 7](#) for all participants). The sponsor may request that the disease assessments be sent for central independent review. Disease evaluations scheduled for treatment days should be collected before study treatment is administered. Disease evaluations will be performed by a central laboratory (unless otherwise

specified) until disease progression or the EOT. This study will use the IMWG consensus recommendations for MM treatment response criteria (Durie et al 2006, Kumar et al 2016, Rajkumar et al 2011) presented in [Table 19](#). Per IMWG uniform response criteria, all response categories and PD require 2 consecutive assessments except for radiographic or bone marrow assessments. For quantitative Ig at baseline, M-protein, IFE, and FLC measurements in serum and 24-hour urine, the investigator will use results provided by the central laboratory. For participants with suspected daratumumab interference on SPEP and IFE, a reflex assay will be performed (see [Appendix E](#)). Participants with confirmed daratumumab interference who meet all other clinical criteria for CR or sCR will be considered CR/sCR.

Table 19: International Uniform Response Criteria Consensus Recommendations

Response	Response Criteria
Stringent complete response (sCR)	
• CR as defined below, plus• Normal FLC ratio, and• Absence of clonal PCs by immunohistochemistry, immunofluorescence,^a or 2- to 4-color flow cytometry.
Complete response (CR) ^b	
• Negative immunofixation on the serum and urine, and• Disappearance of any soft tissue plasmacytomas, and• < 5% PCs in bone marrow.
Very good partial response (VGPR) ^b	
• Serum and urine M-component detectable by immunofixation but not on electrophoresis, or• ≥ 90% reduction in serum M-protein plus urine M-protein < 100 mg/24 hours.

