10.4. Statistical Analyses

10.4.1. Efficacy Analyses

10.4.1.1. Primary Efficacy Analyses

The primary endpoint of the Phase 2 portion of the Protocol is ORR, defined as the proportion of participants with CR, VGPR, or PR, according to IMWG Criteria in the randomized IMWG response evaluable population. Participants will be summarized by treatment group assignment in Phase 2.

The primary analysis of ORR in Phase 2 will compare Treatment Groups A and B modeling the ORR of each treatment group with a Beta (0.5,0.5) prior, calculating the probability that the posterior distribution of the ORR for Treatment Group A exceeds that of the posterior distribution the ORR for Treatment Group B. If $x_1 (n_1)$ is the number of responders (evaluable participants) in Treatment Group A and $x_2 (n_2)$ correspond to the same for Treatment Group B, the resulting posterior distribution will be

$$f_i(\gamma_i | x_i, n_i) = \frac{\Gamma(n_i + 1)}{\Gamma(x_i + 0.5)\Gamma(n_i + 0.5 - x_i)} \gamma_i^{x_i + 0.5} (1 - \gamma_i)^{n_i + 0.5 - x_i}$$

The resulting probability that the ORR for Treatment Group A exceeds that of Treatment Group B, that is, the PPoS, is the quantity

$$\text{PPoS} = \Pr(\text{ORR}_A > \text{ORR}_B | x_1, n_1, x_2, n_2) = \int_0^1 \int_{\gamma_2}^1 f_1(\gamma_1 | x_1, n_1) f_2(\gamma_2 | x_2, n_2) d\gamma_1 d\gamma_2$$

Objective response rate and its 90% Bayesian credible intervals for each treatment group will be presented.

Interim analyses will be conducted after the 31st participant is randomized and after each subsequent participant is to be randomized to adjust the randomization rate between Treatment Groups A and B and to determine whether the study should be terminated for positive efficacy. See Section 10.5.2.1 for details on the conduct of these interim analyses.

If the study does not terminate for early efficacy, the final analysis will take place once all participants have been randomized and monitored for response for 3 months OR once all participants have discontinued the study. If $\text{PPoS} > 0.915$, then the null hypothesis will be rejected, and Treatment Group A will be considered to be superior (with respect to ORR) to Treatment Group B.

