10.5. Interim Analysis

The Statistical Analysis Plan will describe the planned interim analyses in greater detail.

10.5.1. Interim Analysis for Phase 1

In Phase 1, the BOIN design will be used to determine the RP2D of INCB001158 in combination with daratumumab SC. For the design parameters, let ϕ denote the target DLT rate. Let ϕ_1 ($= 0.6\phi$) denote the highest toxicity probability below the MTD so that dose escalation is

required, and ϕ_2 ($= 1.4\phi$) denote the lowest toxicity probability deemed overly toxic so that dose de-escalation is required.

A dose elimination rule is also applied to avoid assigning participants to an overly toxic dose. Let p_j represent the DLT rate, n_j the participants in the treatment group treated at dose level j , and m_j the participants with a DLT at dose level j . If $P_r(p_j > \phi | m_j, n_j) > 0.95$ and $n_j \geq 3$, then dose levels j and higher are eliminated from the dose escalation for the treatment group, and the dose level is terminated if the first dose level is eliminated.

Table 11 (in the bottom row) provides the elimination boundaries for the target DLT rate of 33%, respectively. For example, for the target DLT rate 33%, when the number of participants treated at the current dose $n_j = 4$, we will eliminate that dose and higher doses if 3 or more participants experience toxicity.

Based on the algorithm of the BON design, a minimum of 3 evaluable participants will be enrolled in each dose level with a maximum of 9 evaluable participants in each dose level.

10.5.2. Interim Analysis for Phase 2

10.5.2.1. Efficacy Interim Analysis for Phase 2

In Phase 2, a RAR design will be used to adjust randomization between Treatment Groups A and B and to determine if the study should be terminated for superior efficacy. The first 30 participants will be equally randomized (1:1:1) between Treatment Groups A, B and C. From the 31st participant, adaptive randomization will begin based on the PPoS (as defined in Section 10.4.1.1), comparing Treatment Group A to B ORR using posterior probabilities with the probability of assignment to Treatment Group A being

$$\text{Randomization Probability} = \begin{cases} 0.2 & \text{if } PPoS < 0.2 \\ 0.8 & \text{if } PPoS > 0.8 \\ PPoS & \text{otherwise} \end{cases}$$

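### The interim PPoS admits participants to its denominator from about Day 29-35, before a scheduled visit can confirm a response, so at the protocol's own 3-month response time early stopping is less likely than Table 26 states

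*Protocol*

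**What the plan says.** - **Interim rule (Protocol 10.5.2.1).** "From the 31st participant, adaptive randomization will begin based on the PPoS", and the PPoS is the one defined in 10.4.1.1. The probability of assignment to Group A equals the PPoS, limited to 0.2-0.8, and the study stops for efficacy if the PPoS exceeds 0.9975. Section 6.3 has the IRT update the allocation at each enrollment. No minimum follow-up is given for an interim calculation.
- **PPoS (Protocol 10.4.1.1).** ORR is assessed "according to IMWG Criteria in the randomized IMWG response evaluable population". The PPoS is obtained by "modeling the ORR of each treatment group with a Beta (0.5,0.5) prior", where x (n) "is the number of responders (evaluable participants) in Treatment Group A", and likewise for Group B. Only the final analysis carries a 3-month follow-up condition; its rejection limit is 0.915.
- **Evaluable (Protocol 10.2, Table 27).** Dosed, with a baseline assessment, and any one of: at least one "postbaseline disease assessment"; "Been on the study for a minimum of 35 days of follow-up"; or treatment discontinued.
- **Response (Protocol 8.2.1.1).** "Per IMWG uniform response criteria, all response categories and PD require 2 consecutive assessments except for radiographic or bone marrow assessments". Disease evaluations are scheduled once per 28-day cycle.
- **Simulation (Protocol 10.1.2, Table 26).** Accrual is 4 per month and "the expected number of months between treatment and assessment of response is 3". At 45% v 20% the table gives rejection 78.7%, early termination 30.0% and expected N 71.7.

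**The concern.** A participant enters n about a month after starting treatment, but on scheduled visits cannot enter x until Day 57 and, on the protocol's planning assumption, does so at 3 months. In between, an eventual responder is counted as a failure. The PPoS is recalculated for every assignment from participant 31, so there are always such participants in it. If Group A is doing well it receives up to 80% of recent allocations and so carries more of these provisional failures than Group B.

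At stake are the strength of the adaptation and the reach of the 0.9975 stopping rule. Section 10.5.2.1 points to Table 26 for the likelihood of early termination and the expected sample sizes. If Table 26 was simulated with a different data-maturity rule, those two columns describe another design. The IRT programmer also has no stated rule to build from.

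**Working it through.** **1. Timing.** With 28-day cycles, C2D1 is Day 1 + 28 = Day 29 and C3D1 is Day 1 + 2 × 28 = Day 57. Two consecutive scheduled assessments therefore first confirm a response 56 days after the first dose. An unscheduled repeat could do so sooner.

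**2. Reproducing Table 26.** Inputs, all from Protocol 10.1.2, 10.4.1.1 and 10.5.2.1: posterior Beta(x + 0.5, n − x + 0.5) per arm; PPoS = Pr(ORR_A > ORR_B); 30 participants at 1:1:1, then up to 50 to A or B with Pr(A) = PPoS limited to 0.2-0.8; 4 per month; stop at PPoS > 0.9975; final limit 0.915. Group B response is 20%. Assumed here: evenly spaced accrual, and no early discontinuations. With each participant entering both x and n at 3 months (100,000-150,000 replications per scenario):

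| Group A rate | Rejection %, stated / computed | Early stop %, stated / computed | Expected N, stated / computed |
|---|---|---|---|
| 20% | 9.8 / 9.9 | 1.2 / 1.2 | 79.7 / 79.6 |
| 35% | 50.1 / 50.3 | 12.1 / 12.2 | 76.6 / 76.5 |
| 40% | 65.7 / 65.9 | 19.8 / 19.7 | 74.5 / 74.3 |
| 45% | 78.7 / 79.1 | 30.0 / 29.9 | 71.7 / 71.4 |

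Durations agree to the decimal (22.9, 21.8, 21.0 and 20.0 months). Table 26 thus appears to have been simulated with a 3-month lag for x and n together.

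**3. Changing only entry into n.** Responses still count at 3 months; n follows Table 27.

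| Group A rate | Early stop %, n from Day 35 / C2D1 | Expected N, n from Day 35 / C2D1 | Rejection %, n from Day 35 / C2D1 |
|---|---|---|---|
| 20% | 0.7 / 0.7 | 79.8 / 79.8 | 9.9 / 9.8 |
| 35% | 9.3 / 8.7 | 77.6 / 77.8 | 51.1 / 51.1 |
| 40% | 15.6 / 14.8 | 76.0 / 76.3 | 66.9 / 66.9 |
| 45% | 24.1 / 23.1 | 73.8 / 74.2 | 80.1 / 80.1 |

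Against Table 26, early stopping falls by 2.8-3.4 points at 35%, 4.2-5.0 at 40% and 5.9-6.9 at 45%. Expected N at 45% rises by 2.1-2.5. A smaller run of 6,000 replicates at 45% gave 25.0% (N 73.7) and 23.1% (N 74.2), hence the summary of about 23-25%. With random (Poisson) arrivals the drop is similar: 27.8% with the 3-month lag, 21.5% with n from C2D1.

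**4. Sensitivity to response timing (assumed), 45% v 20%, n from C2D1.**

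| When responses are confirmed | Early stop % | Expected N |
|---|---|---|
| All at Day 56 | 28.8 (29.7 in the 6,000-replicate run) | 71.9 (71.8) |
| 40/35/25% at Days 56/84/112 | 24.3 | 73.7 |
| All at 3 months | 22.9-23.1 | 74.2-74.3 |
| All at Day 112 | 18.7 | 75.7 |

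Early entry alone is not the cause. If n and the response both entered at Day 35, early stopping would be 32.0%. The loss comes from entering n before x can be known.

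**5. How many are immature.** At one participant per 0.25 month, participant 31 is randomized at 30 × 0.25 = 7.5 months. Those with 3 months of follow-up entered by month 4.5: 4.5/0.25 + 1 = 19. Those with at least 29 days (0.95 month) entered by month 6.55, which gives 27. So 8 of 27 are immature across all three groups; Group C does not enter the PPoS, leaving about 8 × 2/3 ≈ 5 in A and B.

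**6. Effect on one PPoS.** With 4/9 v 2/9, PPoS = 0.841. Adding 2 immature participants per arm gives 0.830, and 3 per arm gives 0.826. Adding 3 to A and 1 to B gives 0.755. With 2/9 v 2/9, PPoS = 0.500, and the same 3-v-1 addition gives 0.417. The penalty falls on the arm with more recent allocations.

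**The case against.** Several points against this carry weight.

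- **Timing is assumed.** The documents give one expected time of 3 months and no distribution. If all responses were confirmed at the first scheduled opportunity, the Table 27 rule would nearly recover Table 26. This stands, so the shortfall must be given as a range.
- **The error rates hold.** A reader might infer that Type I error or power in Table 26 is wrong. The documents do not support that: the final analysis waits 3 months, null rejection stays at 9.8-9.9% and power at about 80%. The effect is conservative, with fewer early efficacy stops and no added false positives.
- **Early imbalance is small.** The first 30 are split 1:1:1, so immature participants start about even and the PPoS barely moves (0.841 to 0.830). The larger drop to 0.755 needs an uneven split, which arises as allocation tilts. Nor is the effect a general pull toward 0.5, as the move from 0.500 to 0.417 shows.
- **Detail was deferred.** Protocol 10.5 leaves interim detail to the SAP, and the IRT Manual, which was not available to this review, may hold a data-maturity rule. But SAP 3.1 refers back to the protocol for randomization, and SAP Section 9 says no formal interim analysis will be done, so neither document closes the gap.
- **The point is moot for reporting.** Enrollment has been terminated (Protocol Appendix F, Amendment 3), and SAP 7.2, 7.3.1 and 10.1 cancel the efficacy analyses. This stands, and limits the point to the design specification.

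**Conclusion.** The mismatch is in the text: the interim denominator follows Table 27, while Table 26 reproduces closely in every row when x and n both enter at 3 months. On the protocol's own 3-month time to response, early termination at 45% v 20% is about 23-25% instead of 30.0%, about 3 points lower at 35% and 4-5 lower at 40%. Expected N at 45% is about 74 instead of 71.7, a rise of only 2 to 2.6 participants with the maximum still 80. At 45% v 20% with n from C2D1, early termination ranges from about 29-30% if all responses are confirmed at Day 56 down to 18.7% if all come at Day 112.

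These figures assume 4 per month, no early discontinuations, and the Table 27 rule applied literally. It would go too far to say that Table 26 is wrong as a whole, or that its figures cannot be delivered under any timing: the rejection column holds, and the early-termination column depends on when responses are confirmed. The consequence is weaker adaptation and fewer early efficacy stops. No reported result is affected.

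**What to change.** State in Protocol 10.4.1.1 and 10.5.2.1, and in the IRT specification, that each interim calculation counts in x and n only response-evaluable participants with at least 3 months since randomization, each by response status at 3 months. This is how Table 26 appears to have been simulated, so its figures can then stand. A response or discontinuation known earlier would also wait until 3 months; using it sooner is a different rule and would need its own simulation.

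Alternatively, keep Table 27 for the interims and replace the early-termination and expected-N figures in Table 26 with a re-run that states its response-timing assumption.

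The first option costs one sentence and fewer participants per interim calculation: at participant 31, 19 instead of 27 across the three groups. The second costs a re-run and a lower stated chance of early stopping. With enrollment closed and the SAP's efficacy analyses cancelled, either change corrects the design record, or any reuse of the design, and alters no allocation or result in this study.
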